7.8 SAFETY ANALYSIS

All safety analyses will be performed over the whole trial on the treated set. Similar summaries will be provided regarding the first 48 weeks or the first 96 weeks only.

The analysis of safety data will be based on the concept of treatment emergent AEs or measurements. That means that, for analyses over the whole trial, all AEs/laboratory or vital sign measurements occurring between first nintedanib intake till last nintedanib intake + 28 days will be assigned to the on-treatment period. For analyses over 48 weeks and 96 weeks respectively the on-treatment period is defined from date of first nintedanib intake until date of last nintedanib intake + 28 days, or until Week 48/Week 96 time point (Day 379/ Day 715, i.e. 378/714 days after date of Visit 1), if earlier.

All analyses will be performed according to randomised treatment group in the parent trial and overall.

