6.2.1 Screening and run-in period(s)

Visit 1 will be conducted on the same day as EOT_B of the parent trial, INBUILD[®] so that there is no interruption of treatment. The trial will be explained to all patients who completed INBUILD[®] (who didn't discontinue treatment) and are willing to continue or start treatment with nintedanib. This may be done prior to Visit 1, however no trial related procedure or data collection should be performed until the patient has signed the Informed Consent for the extension trial at Visit 1.

Upon obtaining informed consent, the investigator will register the patient in the IRT system and the patient will receive a trial identification card.

Assessments conducted as part of EOT_B of the INBUILD[®] trial do not need to be repeated for Visit 1 of this extension trial.

If the patient has been determined eligible by the investigator to enter the trial (refer to section [3.3](#)), medication will be assigned to the patient via the IRT system (refer to section [4.1.3](#)). First dose of nintedanib within INBUILD[®]-ON will be administered in the clinic at Visit 1. Data from the EOT_B assessments will be transferred to INBUILD[®]-ON as baseline data. All AEs ongoing at the EOT_B visit of INBUILD[®] will be recorded as baseline conditions in INBUILD[®]-ON.

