5.4.4 Liver enzyme and bilirubin elevations

Liver enzyme and bilirubin elevations will be reported using the following definitions:

- (ALT and/or AST >=3 fold ULN) and bilirubin >=2 fold ULN ^[1]
- ALT >=5 fold ULN and/or AST >=5 fold ULN
- ALT >=3 fold ULN and/or AST >=3 fold ULN

^[1] within a time window of 30 days i.e. the elevation of bilirubin should appear within 30 days after the elevation of AST and/or ALT

The proportion of subjects presenting signs of hepatic injury will be summarised, based on the following definition for signs of hepatic injury:

- ALT and/or AST ≥ 8 fold ULN
- ALT and/or AST ≥ 3 fold ULN and total bilirubin ≥ 2 fold ULN ^[2]
- ALT and/or AST ≥ 3 fold ULN and unexplained INR > 1.5 ^[2]
- ALT and/or AST ≥ 3 fold ULN and unexplained eosinophilia ($> 5\%$) ^[2]
- ALT and/or AST ≥ 3 fold ULN and appearance of fatigue, nausea, vomiting, right upper abdominal quadrant pain or tenderness, fever and/or rash within $+/- 7$ days of the abnormal ALT and/or AST laboratory test result (please refer to [Table 9.3: 1](#) for the list of relevant MedDRA preferred terms to support the derivation of a potential hepatic injury)

^[2] in the same blood draw sample

In addition, maximum individual elevations based on worst value on treatment will be defined as:

- ≥ 3 fold ULN; ≥ 5 fold ULN; ≥ 8 fold ULN for AST and ALT and AST and/or ALT
- ≥ 1.5 fold ULN; ≥ 2 fold ULN for Bilirubin
- $\geq 1.5 \times$ ULN; ≥ 2 fold ULN for alkaline phosphatase (ALK)
- $\geq 3 \times$ ULN for Gamma-Glutamyl-Transferase (GGT)

Note: ULN refers to the Upper Limit of Normal from the central or local laboratory analysing samples from this extension trial.

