5.4.4.1 Time-to-event analyses for liver enzyme elevations

Time to first occurrence in extension trial of the above described liver enzyme elevations [days] will be analysed as

Date of event/censoring - Date of first nintedanib intake + 1 day

Subjects with no such event occurred during the trial will be censored according to the mechanism for censoring as described in [Table 5.4.4.1: 1](#).

These times to onset of first event in extension trial will also be summarised in categories:

- <=1 month (31 days)
- >1 to <=3 months (91 days)
- >3 to <=6 months (182 days)
- >6 to <=12 months (365 days)
- >12 to <=18 months (547 days)
- >18 to <=24 months (730 days)
- >24 to <=36 months (1095 days)
- >36 months
- Censored

Further categories might be defined if needed.

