6. GENERAL ANALYSIS DEFINITIONS

6.1 TREATMENTS

For treatment specifications, please refer to CTP Section 4.

The different periods of interest, as per CTP flow chart, are the following:

Note: the last day of each of the periods is excluded from the period. It defines the first day of the subsequent period.

- Post-IC period (optional^[a]): From date of informed consent to first nintedanib intake.
- Treatment period: From first nintedanib intake (or re-start of treatment if interruption) to last nintedanib intake (or day before start date of interruption if interruption) plus one day.
- Off-treatment (optional^[a]): From start date of interruption to re-start of treatment.
- Residual effect period^[b]: From last nintedanib intake plus one day to last nintedanib intake plus 28 days plus one day.
- Follow-up period (optional^[a]): From last nintedanib intake plus 28 days plus one day (after residual effect period) to last contact date (as collected on the end of study eCRF page) plus one day. This period is only created if last nintedanib intake took place more than 28 days before last contact date (as collected on the end of study eCRF page).
- Post-study period (optional^[a]): From last nintedanib intake plus 28 days plus one day or from last contact date (as collected on the end of study eCRF page) plus one day, whichever occurs later.

^[a] This period is optional insofar as it does not necessarily exist for all subjects.

^[b] In addition, a residual effect period of 7 days will be used for safety analyses to more closely reflect the period of time after the last nintedanib intake.

For subjects who did not receive any dose of nintedanib in extension trial, Post-IC period is the only period defined.

For subjects who died during the trial, periods with above defined start date after date of death do not exist and last existing period is defined until date of death plus one day only.

For safety analyses ([Section 7.8](#)), data from the treatment period, possible off-treatment periods and residual effect period will be considered as on-treatment.

6.2 **IMPORTANT PROTOCOL DEVIATIONS**

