6.7 BASELINE, TIME WINDOWS AND CALCULATED VISITS

As a general rule, the last assessment/measurement before or on the date of Visit 1 will be used as baseline.

Visit windowing will be performed as described in [Tables 6.7: 1, 6.7: 2](#) and [6.7: 3](#), in order to assign data to the relevant study visit based on the actual day of the assessment. Data will be analysed using the re-calculated visits in the statistical tables. However, in the listings, all visits performed will be displayed (even if outside time-window), along with the re-calculated visit. No time-windowing will be performed for the follow-up visit, i.e. follow-up visit will be displayed in listings (where applicable) whenever it was performed. A follow-up visit is only scheduled for subjects who prematurely discontinued nintedanib due to adverse event.

Table 6.7: 2 Time windowing rules for physical exam and vital signs

Time window of actual day ^[1]			Allocated to		
Start day	End day (included)	Length of the time-window [days]	Visit number	Visit name	Planned day of the visit
1	1	1	1	Baseline	1
2	22	21	2	2 weeks	15
23	43	21	3	4 weeks	29
44	71	28	4	8 weeks	57
72	127	56	5	12 weeks	85
128	211	84	6	24 weeks	169
212	295	84	7	36 weeks	253
296	379	84	8	48 weeks	337
380	463	84	9	60 weeks	421
464	547	84	10	72 weeks	505
548	631	84	11	84 weeks	589
632	715	84	12 (p)	96 weeks	673 (V _p)
$\frac{V_p + 1}{2} + \frac{V_{p+1} - V_p}{2}$	$\frac{V_{p+1}}{2} + \frac{V_{p+2} - V_{p+1}}{2}$	$\frac{V_{p+2} - V_p}{2}$	p + 1	...	$V_{p+1} = V_p + 12 \times 7$
...	Every 12 weeks thereafter	...

V_p denotes the planned day of the visit

[1] Date of Visit 1 in extension trial is taken into account as a reference to calculate time windows

Table 6.7: 3 Time windowing rules for laboratory measurements (and pregnancy test)

Time window of actual day ^[1]			Allocated to		
Start day	End day (included)	Length of the time-window [days]	Visit number	Visit name	Planned day of the visit
1	1	1	1	Baseline	1
2	22	21	2	2 weeks	15
23	43	21	3	4 weeks	29
44	71	28	4	8 weeks	57
72	106	35	5	12 weeks	85
107	148	42	5a ^[2]	18 weeks	127
149	190	42	6	24 weeks	169
191	232	42	6a ^[2]	30 weeks	211
233	274	42	7	36 weeks	253
275	316	42	7a ^[2]	42 weeks	295
317	379	63	8	48 weeks	337
380	463	84	9	60 weeks	421
464	547	84	10	72 weeks	505
548	631	84	11	84 weeks	589
632	715	84	12 _(p)	96 weeks	673 (V_p)

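### Liver-enzyme elevations already present at Visit 1 can be reported as first on-treatment elevations, because the SAP's liver definitions carry no baseline condition and its date rules give the Visit 1 sample two roles

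*SAP*

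**What the plan says.** **Entry.** The extension's own criteria (protocol 3.3.2 and 3.3.3) set no ALT, AST or bilirubin limit. Exclusion criterion 1 sends the investigator back to the INBUILD list in Appendix 10.1, which includes AST/ALT above 1.5x ULN, bilirubin above 1.5x ULN and chronic liver disease. It also allows entry when a criterion was met during INBUILD, if the investigator still judges benefit-risk favourable. SAP Table 6.2: 1 makes entry with exclusion 1 met an important deviation (A2) but excludes such subjects from no analysis.

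**Timing.** Under flowchart footnote 2, the Visit 1 laboratory tests are done once, as part of EOT_B in INBUILD, on the same day as Visit 1. Protocol 6.2.1 adds that the first dose "will be administered in the clinic at Visit 1".

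**Periods and baseline.** SAP 6.1 runs the pre-treatment period "From date of informed consent to first nintedanib intake" and states that "the last day of each of the periods is excluded from the period. It defines the first day of the subsequent period". For laboratory values over the whole trial, SAP 7.8 then says that "measurements occurring between first nintedanib intake till last nintedanib intake + 28 days will be assigned to the on-treatment period". SAP 6.7 says that "the last assessment/measurement before or on the date of Visit 1 will be used as baseline".

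**Liver definitions.** SAP 5.4.4 uses fixed multiples of the ULN for ALT, AST, bilirubin, ALK and GGT, and "maximum individual elevations based on worst value on treatment will be defined as" such multiples. SAP 5.4.4.1 begins "Time to first occurrence in extension trial of the above described liver enzyme elevations [days] will be analysed as" and gives the event or censoring date minus the date of first intake, plus one day. Neither section mentions the baseline value.

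**The concern.** SAP 7.8 rests the safety analysis on a treatment-emergent concept for measurements as well as adverse events. A liver value that was already raised when the patient entered is not treatment-emergent in the extension, yet nothing in the liver definitions removes it.

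The two parent-trial groups are affected differently. In a former placebo patient, an elevation that arose on placebo would appear as an elevation on nintedanib. In a former nintedanib patient, an INBUILD finding would appear again as a first occurrence in the extension. Results are shown by parent-trial group, so both errors land where a reader looks for the effect of starting versus continuing the drug. Hepatic injury is a protocol-specified adverse event of special interest, and protocol 1.2 says most hepatic events occur in the first three months of treatment. That is the part of the time axis where carried-over elevations would fall.

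**Working it through.** The plan states no figure on this point, so there is none to reproduce. The check applies the SAP's rules to a blood draw and then illustrates the size.

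**1. Date rules.** Take consent, blood draw and first dose on one date (protocol flowchart and 6.2.1). Apply the SAP 6.1 periods, the Table 6.7: 3 windows and the SAP 5.4.4.1 formula (event date − first intake date + 1).

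| Study day of draw | Period (6.1) | Window (Table 6.7: 3) | Time to event (5.4.4.1) |
|---|---|---|---|
| 1 | Treatment | Baseline | 0 + 1 = 1 day |
| 2 | Treatment | Visit 2 | 1 + 1 = 2 days |
| 15 | Treatment | Visit 2 | 14 + 1 = 15 days |

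The Day 1 draw is on-treatment by period and baseline by window. The two rules conflict, and the SAP does not say which governs the liver tables and curves.

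**2. Persistence.** Suppose ALT is 3.5x ULN on Day 1 and still 3.5x ULN on Day 15. Read Day 1 as baseline only. The Day 15 value is on-treatment and post-baseline under every rule, it meets the 3-fold threshold, and no condition looks back at Day 1. The subject is an event at 15 days, within the first-month category (31 days or less). If Day 1 counts, the event is at 1 day, in the same category. Resolving Day 1 alone therefore does not settle the matter.

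**3. Comparison within the SAP.** Other analyses carry the condition that is missing here:
- A marked vital-sign increase (5.4.5) needs both a threshold and a minimum rise above baseline.
- Time to first dose reduction (7.7) is limited to subjects who start at 150 mg, that is, those at risk of the event.
- Abnormalities present at Visit 1 are recorded as baseline conditions and not as adverse events (protocol 5.2.5.1.1).

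**4. Size.** The only input from the documents is the planned number, about 480. Prevalence p (ALT or AST at or above 3x ULN at Visit 1) and persistence q (the share still elevated at the next draw) are assumptions. Subjects carried over = 480 × p if Day 1 counts, and 480 × p × q if it does not.

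| p (assumed) | Day 1 counted | Day 1 not counted, q = 0.5 |
|---|---|---|
| 0.5% | 480 × 0.005 = 2.4 | 1.2 |
| 1% | 480 × 0.01 = 4.8 | 2.4 |
| 2% | 480 × 0.02 = 9.6 | 4.8 |
| 3% | 480 × 0.03 = 14.4 | 7.2 |

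On the reported percentage this is 0.5 to 3 points, or 0.25 to 1.5 points with Day 1 excluded and half persisting. These are upper limits for each p and q, since some of these subjects might also have a genuine new elevation later.

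**The case against.** **Entry is screened.** A reader might infer that no rule keeps out patients with raised enzymes. The documents do not support that: exclusion 1 with Appendix 10.1 is such a rule, and entering against it is flagged as a deviation. What stands is that the rule is discretionary. Nor do the documents require the Visit 1 result before dosing on that day, and the sample goes to a central laboratory (protocol 5.2.3).

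**Day 1 may never be counted.** A reader might also infer that the Day 1 sample is certainly booked as on-treatment. It is taken as part of EOT_B, is plausibly drawn before the dose, is transferred as baseline data, and falls in a window labelled Baseline only. If clock times were used, counting from first intake would exclude it. Against that, 7.8 defines the 48- and 96-week periods from the date of first intake, 5.4.4.1 works in dates, and Table 6.7: 3 only assigns values to visits. Day 1 is an unresolved conflict, not a proven double count.

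**Some rules are not visible.** SAP 7.8.2.1 defers standard laboratory handling to a company standard, and the censoring table cited in 5.4.4.1 is not in the public text. Either might contain a baseline rule. The liver definitions themselves do not point to one.

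**Worst value against the ULN is a legitimate, conservative display.** This is true, and 7.8.2.2 also plans individual profiles for subjects at or above 3x ULN. Profiles let a reader see a carried-over case but do not correct the counts or curves.

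**Restricting to subjects below threshold can hide a recurrence.** Someone elevated at entry who normalises and rises again would be lost by simple exclusion. This objection stands, and the fix has to allow for it.

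**Conclusion.** The point holds as a gap in the liver-elevation analyses. Its firm part is the absence of a baseline condition in SAP 5.4.4 and 5.4.4.1: on the text available, an elevation present at Visit 1 that persists to a later draw is counted as a first on-treatment elevation, contrary to the concept stated in 7.8. The less certain part is the double role of the Visit 1 sample, which the SAP leaves unresolved.

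Affected are the elevation and worst-value tables, the first-month category and the start of the Kaplan-Meier curves. A reader might infer that the primary endpoint is affected too. It is not: it counts adverse events, and findings already present at Visit 1 are recorded as baseline conditions. All analyses are descriptive, so no test or decision rule changes.

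The size is unknown. About 2 to 14 subjects follows only from assuming 0.5% to 3% prevalence among 480, and 1.2 to 7.2 if Day 1 is excluded and half persist. The upper end may be generous for former placebo patients: INBUILD reported hepatic-enzyme adverse events in 5.7% on placebo over a full 52 weeks, although that is a different measure. A reader might set these counts against a guessed number of new elevations and quote a large relative inflation. The documents give neither quantity, so no relative figure is offered.

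**What to change.** - In SAP 5.4.4, 5.4.4.1, 7.8 and 7.8.2.2, state that the measurement used as baseline is pre-treatment and is never an on-treatment value.
- For each threshold, present the number and percentage with an elevation, and the time to first elevation, in subjects below that threshold at baseline.
- Show subjects at or above the threshold at baseline on a separate line by parent-trial group, and identify there any who normalise and rise again.

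Because the condition is threshold-specific, a subject at 3.5x ULN at baseline who later reaches 9x ULN still counts on the main lines for 5x and 8x ULN, so worsening stays visible.

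The cost is SAP wording and a programming condition, with no new data. The downside is slightly smaller denominators for the main lines and extra table lines. No change to eligibility or patient management is proposed.

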7.8.1 Adverse Events

Adverse events will be coded using the current Medical Dictionary for Regulatory Activities (MedDRA) version in use at BI at the time of database lock. Unless otherwise specified, the analyses of AEs will be descriptive in nature. All analyses of AEs will be based on the number of subjects with AEs and NOT on the number of AEs.

For analysis multiple AE occurrence data on the eCRF will be collapsed into an AE provided that all of the following applies:

- All AE attributes are identical (Low Level term ((LLT), intensity, action taken, therapy required, seriousness, reason for seriousness, relationship, outcome, AESI, CTCAE if applicable)
- The occurrences were time-overlapping or time-adjacent (time-adjacency of 2 occurrences is given if the second occurrence started on the same day or on the day after the end of the first occurrence).

For further details on summarization of AE data, please refer to ([6](#), [7](#)).

All AEs occurring before first nintedanib intake will be assigned to 'Post-IC period' and all AEs occurring after the residual effect period will be assigned to 'follow-up' or 'post-study' (for listings only). All adverse events occurring between the start and the end of an interruption of nintedanib will be assigned to 'off-treatment' period in the listings. For details on the treatment definition, see [Section 6.1](#).

According to ICH E3 ([2](#)), AEs classified as 'other significant' need to be reported and will include those non-serious and AEs with
(i) 'action taken = DRUG WITHDRAWN' or 'action taken = DOSE REDUCED', or
(ii) marked haematological and other lab abnormalities or lead to significant concomitant therapy.

Summary tables will be produced for non-serious adverse events meeting part (i) of the definition. Part (ii) of the definition will be covered by the analysis of laboratory data. Please refer to [Section 7.8.2](#) for further information.

Adverse events related to gastrointestinal perforation and hepatic injury will be considered as protocol-specified AEs of special interest (AESIs), and ticked as such in the eCRF.

Table 7.8.1: 1 Protocol-specified AESI

Protocol-specified AESI	AE type
Gastrointestinal perforation	AEs established for other tyrosine kinase inhibitors as possible adverse reactions
Hepatic injury	Other AEs of interest

An overall summary of AEs will be presented, by treatment group in the parent trial and overall.

The frequency of subjects with adverse events, will be summarised by randomised treatment group in parent trial (and overall), primary system organ class (SOC) and preferred term (PT). This will be repeated for subjects with adverse events occurring with an incidence in preferred term greater than 5% (in at least one treatment arm). For analyses over the whole trial, time at risk and exposure-adjusted incidence rates with 95% confidence intervals will be presented in addition. Please refer to [Section 7.8.1.1](#) for further details on the derivation of time at risk and exposure-adjusted incidence rates.

Separate tables will be provided for subjects with

- serious AEs (SAEs)
- severe AEs
- other significant AEs (as defined by point (i) of the ICH E3 definition indicated above)
- AEs leading to dose reduction
- AEs leading to permanent treatment discontinuation
- investigator defined drug-related AEs
- AEs leading to death
- protocol-specified AEs of special interest (AESIs)
(as ticked on the AE page of the eCRF)
- investigator defined drug-related SAEs.

The system organ classes (SOC) will be sorted according to the standard sort order specified by EMA, preferred terms will be sorted by decreasing frequency in the total column (within SOC).

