4.2.1.1 Management of diarrhoea

Diarrhoea is a known side effect of nintedanib treatment (see section [1.2](#)). However, potential causes for diarrhoea other than study medication should always be considered and treated accordingly (e.g. viral infections, bacterial overgrowth, antibiotic treatment).

Diarrhoea should be managed as early as possible after onset of first symptoms with standard antidiarrhoeal symptomatic treatment, e.g. loperamide.

If diarrhoea persists despite optimal symptomatic treatment, treatment interruption and dose reduction of nintedanib should be considered based on the recommendations described in table 4.2.1.1:1.

Table 4.2.1.1: 1 Management of diarrhoea (considered related to trial medication)

Description	Symptomatic Treatment*	Action with trial medication
Diarrhoea with increase of <4 stools per day over baseline ¹ .	Initiate anti-diarrhoeal medicines at first signs of symptoms (e.g. 4 mg loperamide followed by 2 mg after each loose stool or every 2-4 hours to a maximum of 16 mg/day) until bowel movements cease for 12 hours.	Continue same trial medication dose.
Diarrhoea with increase of 4 to 6 stools per day over baseline ¹ .	Initiate/continue anti-diarrhoeal medicines; If diarrhoea of this severity persists for ≥48 to 72 hours assess for dehydration and electrolyte imbalance; In addition, consider IV fluids and electrolyte replacement as clinically indicated.	If diarrhoea persists for ≥48 to 72 hours despite optimal symptomatic care: 1. Interrupt trial medication until recovery. 2. Reduce dose to 100 mg bid after recovery. 3. Re-escalate to 150 mg bid within 4 weeks if deemed clinically appropriate.
Diarrhoea with increase of ≥7 stools per day over baseline ¹ ; stool incontinence, or life threatening consequences.	Follow recommendations above. In addition, consider stool work-up to exclude infectious colitis; adequate IV fluid replacement ≥24 hours, hospitalisation as clinically indicated; consider referral to a GI specialist to rule out potential differential diagnoses.	1. Interrupt trial medication until recovery. 2. Reduce dose to 100 mg bid after recovery. 3. Consider re-escalation within 4 weeks to 150 mg bid if deemed clinically appropriate. In case of reoccurrence of diarrhoea of this severity despite optimal symptomatic treatment and dose reduction, treatment with trial medication should be permanently discontinued.

Footnotes:

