7.7 EXTENT OF EXPOSURE

Exposure will be summarised over the whole trial. Similar summaries will be provided regarding the first 48 weeks or the first 96 weeks only.

A summary table showing the duration on treatment in extension trial in months (both, mean and frequency in categories, see [Section 5.4.3](#)) will be presented together with duration of exposure in patient-years, total dose (mean) and dose intensity (both, mean and frequency in categories, see [Section 5.4.3](#)).

Besides, a summary table showing the duration on actual treatment dose in months (both, mean and frequency in categories, see [Section 5.4.3](#)) and off-treatment duration in weeks (mean) will be performed. This will take into account the actual dose following dose reductions or increases. Furthermore, the proportion of subjects on each dose actually taken as first dose in 1199-0248 will be presented.

A summary of dose reductions will be performed including number of subjects with at least one dose reduction, number of dose reductions (total and per subject) and reasons for dose reduction, as well as time to first dose reduction in extension trial (both, quartiles from Kaplan-Meier curve and frequency in categories, see [Section 5.3.3.3](#)). Dose intensity of subjects with at least one dose reduction will be summarised in addition. A similar summary will be performed for treatment interruptions. Additionally, the (total) duration of interruptions per subject will be summarised. For dose increases to 150 mg only number of subjects with at least one increase and total number of increases will be summarised.

Time to first dose reduction will only be calculated for subjects with first dose in extension trial 150 mg (see [Section 6.3](#) for further information on this analysis set).

As for the other exposure-related time-to-event analyses, time to premature treatment discontinuation and time to first dose reduction or treatment interruption will be summarised over the whole trial on the Treated Set according to both, quartiles from Kaplan-Meier curve and frequency in categories (see [Section 5.4.3.1.1](#)).

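### SAP 7.8.1 assigns AEs that led to significant concomitant therapy to laboratory data that cannot show them, and plans no SOC/PT table of AEs leading to interruption

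*SAP*

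**What the plan says.** SAP 7.8.1 defines other-significant AEs, citing ICH E3, and says that they need to be reported. The first part reads "i) 'action taken = DRUG WITHDRAWN' or 'action taken = DOSE REDUCED', or". The second part covers "marked haematological and other lab abnormalities or lead to significant concomitant therapy". Non-serious AEs meeting part (i) get summary tables. For the second part the SAP says: "Part (ii) of the definition will be covered by the analysis of laboratory data", and points to 7.8.2.

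The same section then lists nine separate AE tables. They include "AEs leading to dose reduction" and AEs leading to permanent discontinuation. None is for AEs leading to interruption.

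Interruption is taken up in SAP 7.7, after a dose-reduction summary that gives subjects, counts, reasons and time to first reduction: "A similar summary will be performed for treatment interruptions". Total duration of interruptions per subject is added.

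Protocol 4.2.1 names dose reduction and interruption side by side as ways to manage AEs. For diarrhoea, Table 4.2.1.1:1 starts with "Initiate anti-diarrhoeal medicines at first signs of symptoms". When trial drug is acted on in the two higher tiers, the first step is "Interrupt trial medication until recovery", followed by reduction to 100 mg bid.

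**The concern.** The main objective is long-term tolerability and safety. In an open-label trial without a control arm, much of what can be learned about tolerability is which events made patients pause, reduce or stop the drug, and which needed treatment. The SAP shows the event behind a reduction or a stop. It does not show the event behind a pause, and it assigns treated events to an analysis that has no treatment information.

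The parent-trial figures in Protocol 1.2 show why the middle ground matters. Over 52 weeks 66.9% of nintedanib patients had diarrhoea, while the gastrointestinal AEs led to premature discontinuation in less than 10% of patients. Much of that burden was therefore managed without stopping the drug.

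**Working it through.** No arithmetic applies: all analyses are descriptive, and the SAP states no figure to reproduce on this point. The check is to trace each way of handling an AE to its planned outputs.

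**Step 1: can 7.8.2 deliver part (ii)?** Section 7.8.2.1 covers laboratory measurements and reference ranges. Section 7.8.2.2 covers liver enzyme and bilirubin elevations: tables, time to onset, individual profiles and plots. Neither uses a treatment variable. The laboratory half of part (ii) is covered; the therapy half is not. Section 7.2.2 tabulates therapies by ATC class and by customised drug grouping, with no stated link to the AE treated, so it does not supply the missing output either.

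**Step 2: which actions have an AE table?**

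| How the AE was handled | Output outside the AE tables | SOC/PT table by action (7.8.1) |
|---|---|---|
| Dose reduced | 7.7: counts, reasons, time to first | Yes |
| Drug stopped permanently | 7.1: completion status and reasons; 7.7: time to premature discontinuation | Yes |
| Drug interrupted | 7.7: counts, time to first, duration and, by analogy, reasons | None |
| Treated with concomitant therapy | 7.2.2: therapies, no AE link stated | None; assigned to laboratory data |

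Dose reduction gets both an exposure summary and an AE table. Interruption gets only the exposure summary.

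**Step 3: which protocol pathways fall into the gap?**

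- *Diarrhoea, lowest tier.* Symptomatic treatment is given and trial drug continues. Only a therapy table could mark the event as treated.
- *Diarrhoea, higher tiers, patient on 150 mg bid.* Interruption is followed by reduction. The event reaches the reduction table if the action taken is recorded as reduced. The SAP gives no rule for an AE that led to both.
- *ALT/AST 3x to <5x ULN (Table 4.2.1.2:1).* Reduction or interruption. Reduction is tabulated.
- *ALT/AST 5x to <8x ULN without signs of hepatic injury.* Interruption, then restart at the reduced dose if values fall below 3x ULN. The same coding question arises.
- *Patient already on 100 mg bid.* Protocol 4.2.1 allows no further reduction. An AE handled by interruption and restart reaches neither action table.
- *AE not considered drug related.* Table 4.2.1:1 allows up to 12 weeks of interruption and recommends restart at the same dose. It also reaches neither action table.

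The last two pathways are certain gaps. The second and fourth depend on how the action taken is coded.

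**Step 4: are the data there?** SAP 7.8.1 names action taken and therapy required among the AE attributes when it sets the rule for collapsing AE records. Both tables can be built from existing fields.

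**The case against.** The strongest reply is that little is lost. Every treatment-emergent AE appears by SOC and PT, with exposure-adjusted rates over the whole trial. Serious, severe and drug-related AEs have their own tables. Diarrhoea also has a SOC/PT summary, an AE-level summary of its extra eCRF details and a Kaplan-Meier plot (7.8.1.3), and liver elevations are described at length (7.8.2.2). Interruptions are counted and timed in 7.7. For patients on 150 mg bid the drug-related pathways usually end in a reduction, which is tabulated. SAP 7.8.1 also defers detail to sponsor guides that are not part of these documents and might include an interruption table.

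Most of this stands, and it rules out stronger readings. A reader might infer that the protocol's first steps for diarrhoea and liver enzymes are missing altogether, or that tolerability would be judged only on later, rarer actions. The documents do not support either. Reduction is a first-step option at 3x to <5x ULN and is tabulated, the events themselves are named in the SOC/PT tables, and the items in the diarrhoea summary are not listed, so its content cannot be called absent. A diarrhoea event interrupted and restarted at the same dose would also not follow Table 4.2.1.1:1 unless the patient was already on 100 mg bid.

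The reply does not rescue the part (ii) sentence. It says where the output will come from, and that source cannot provide it. Nor does it explain why reduction gets an AE table and interruption does not. The diarrhoea summary cannot stand in, because 7.8.1.3 covers diarrhoea, bleeding and ILD but not nausea, vomiting or liver enzymes.

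**Conclusion.** The part (ii) sentence is wrong as written: a category that the SAP says must be reported has no output that can show its non-laboratory therapy component. The missing interruption table is a smaller matter, a cheap improvement rather than an error.

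The size is limited. The primary endpoint, overall AE incidence, is unaffected, and no event disappears from the report. What is lost is the cross-tabulation of event by action for AEs handled by interruption alone, and of event by treatment for treated AEs. The documents give no interruption rate, so the number of patients cannot be estimated from them. The parent-trial percentages show only that much diarrhoea was managed short of stopping. They do not transfer directly: patients who stopped early in the parent trial are excluded here, and AEs ongoing at entry become baseline conditions.

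The conclusion assumes that the sponsor guides add no interruption table that the SAP leaves unmentioned. The remedy assumes that the action-taken field has a value for interruption; the SAP names only the values for withdrawal and reduction.

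**What to change.** Make four changes in SAP 7.8.1:

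1. Limit the laboratory sentence to the marked-abnormality component of part (ii).
2. Add one SOC/PT table of AEs with action taken recorded as drug interrupted, by parent-trial treatment group and overall, in the layout of the dose-reduction table.
3. Report the therapy component of part (ii) from the therapy-required attribute. Label the table as AEs requiring therapy, because that attribute is broader than significant therapy and may include minor treated events.
4. Add a footnote to the interruption and reduction tables saying how an AE that led to both is counted.

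No new data collection is needed, and no linkage of AEs to dose-change records. The cost is SAP wording, two further tables and a slightly longer table set.
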